5.2 STUDY POPULATION

5.2.1 SAMPLE SIZE CALCULATION

The sample size required for a 2-tailed matched paired t-test to detect a difference of at least 5 points in subjective ratings, with $\alpha=0.05$, power = 0.95, and $\text{diff}/\text{SD} = 0.60$ is 39 (Figure 1).

Therefore, a sample size of 43 is being proposed to account for possible dropouts and screen failures (for which not all visits are required).

[figure not shown]

Figure 1: Sample size calculation

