5.2.2 NUMBER OF PARTICIPANTS

Up to 60 participants may be screened using CORE records and advertising approved by the UW Office of Research Ethics. Approximately 43 participants will be dispensed / randomized with study products, with a target of number of 39 participants completing the study. Informed consent will be obtained for all participants prior to their enrolment in the study (Appendix 1).

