- Participants will be provided with a subjective rating questionnaire (related to comfort, dryness, handling, onset time of discomfort, total wear times and reasons for lens removal) to be completed at home on Days 1, 3 and 5. Participants will be instructed that they must wear the lenses on the days where they are required to complete the ratings, and will be scheduled to return for their next visit between 6 and 14 days after the screening visit.

Visit 2 (Day 0 for DT1): Review habitual DD lenses and dispense DT1, 6-14 days after V1 (1.0 hour)

- Participants will attend this visit wearing their habitual DD CLs for \geq 2 hours prior to the visit.
- The subjective ratings completed at home will be reviewed.
- In-office subjective ratings of a typical day for comfort, dryness, vision and handling (with CLs; 0 to 100 scale), plus total wear time and comfortable wear time (onset time of discomfort) per day over the last month.

- The following assessment of the habitual lenses will be made:
 - Distance HCHI visual acuity, OD, OS & OU;
 - Lens surface characteristics: wettability and deposition;
 - Lens fit.
- After lens removal, a slit lamp biomicroscopy examination (including assessments for ocular surface staining and hyperemia) will be performed.
- DT1 will be dispensed and the following assessments will be made:
 - Distance HCHI visual acuity, OD, OS & OU;
 - Lens surface characteristics: wettability and deposition;
 - Lens fit.
- Participants will be provided with a 1 month supply of overlabeled DT1 CLs (for masking) and instructed to wear the lenses at least 3 days per week and 6 hours per day throughout the study.
- Participants will be provided with a subjective rating questionnaire (related to comfort, dryness, handling wear times and reasons for lens removal) to complete at home on Days 1, 3, 5, 7, 21, 28. Participants will be instructed that they must wear the study lenses on the days where they are required to complete the ratings, and will be scheduled to return for their next visit between 29 and 34 days after V2.

Visit 3: Review DT1 and study exit, day 29-34 days after V2

- Participants will attend this visit wearing the study CLs for \geq 2 hours prior to the visit.
- Participants will be asked to complete a CLDEQ-8 questionnaire to review their experience with the DT1 study lenses.
- The subjective ratings completed at home will be reviewed.

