5.5.2 QUESTIONNAIRES AND SUBJECTIVE RATINGS

Questionnaires:

At the screening visit (Visit 1), participants will complete the OSDI questionnaire to reflect their dry eye symptoms.

At visits 1 and 3, participants will complete the CLDEQ-8 questionnaire, reporting their experience with their habitual and study contact lenses, respectively, over the past 2 weeks.

Subjective ratings:

Participants will be provided with subjective rating 0-100 questionnaires related to comfort, dryness, vision, lens handling and will be asked for times of lens insertion and removal and reasons for lens removal as well as onset of discomfort on that day and reason for lens removal. This questionnaire will be completed at home on Days 1, 3, 5 after visit 1 and on Days 1, 3, 5, 7, 21, 28 after visit 2. Participants will be instructed that they must wear the study lenses on the days where they are required to complete the ratings, and will be scheduled to return for their next visit.

The same questionnaire will be provided to the participants during visit 1 and 3 to reflect their overall 'typical day' experience over the previous month.

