11 STATISTICAL ANALYSIS AND DATA MANAGEMENT

11.1 STATISTICAL ANALYSIS

All data will be analyzed by CORE at the University of Waterloo. Descriptive statistics will be provided on information regarding baseline variables (e.g. age, gender). Differences between lenses and differences over time will be compared using either Paired t-tests or Wilcoxon matched pairs, or using ANOVA, as applicable; statistical significance will be set at 5%. The appropriate tests will be selected based on tests of normality - non-parametric tests will be used for data not showing a normal distribution. For assessments conducted for each eye separately, the right eye will be used for analysis.

The following statistical tests will be performed for the listed comparisons after 1 month of DT1 wear vs habitual DD CL wear (Table 4).

Table 4: Statistical procedures

Comparison	Statistical test
CLDEQ-8 ratings between lenses (habitual DD vs. DT1)	2-sided paired t-test
Subjective ratings between lenses (habitual DD vs. DT1)	2-sided paired t-test

Subjective ratings over time (from home ratings) for DT1	Repeated Measures ANOVA
Comparisons as above, but on groups stratified by DED subtype (evaporative/aqueous deficient/mixed disease)	2-sided paired t-test

In addition, equivalence and superiority for the test lens (DT1) vs the habitual lens will be evaluated for the primary outcome variables, with a change in subjective ratings of 5 points and a difference of 0.5 hours in average and comfortable wear time being considered as a clinically relevant difference.

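### Repeated-measures ANOVA on the six DT1 home ratings by default drops anyone with a missing day, and no sphericity correction is named; a mixed model on all ratings avoids both problems

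*Combined protocol and SAP*

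**What the plan says.** Table 4 in section 11.1 has a row for "Subjective ratings over time (from home ratings) for DT1", and the test entered against it is "Repeated Measures ANOVA". The text above the table adds that "statistical significance will be set at 5" per cent.

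The rating days are fixed in section 5.4.2 under Visit 2 ("to complete at home on Days 1, 3, 5, 7, 21, 28") and repeated in section 5.5.2 ("on Days 1, 3, 5, 7, 21, 28 after visit 2").

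The only model assumption that section 11.1 deals with is normality: "non-parametric tests will be used for data not showing a normal distribution". It names no sphericity test or correction, no covariance structure, no analysis set for this row, and no rule for a participant who lacks one or more home ratings.

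On numbers, section 5.2.1 says that "a sample size of 43 is being proposed to account for possible dropouts and screen failures". Section 5.2.2 speaks of about 43 dispensed, "with a target of number of 39 participants completing the study".

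**The concern.** Two features of the classical method matter here.

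**Missing ratings.** The univariate repeated-measures ANOVA works on complete rows. With six self-completed ratings at home, one missed day removes a participant's other five ratings. A participant who stops DT1 before Day 28 can never have a complete row. Section 9 lists unacceptable comfort with the study product and persistent symptoms among the reasons for discontinuation, so this loss can depend on the very outcome being rated. The day-by-day means would then describe those who tolerated the lens and kept up the diary.

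**Sphericity.** The uncorrected F-test holds its 5% level only if all differences between pairs of days have the same variance. The gaps between ratings are 2, 2, 2, 14 and 7 days. If ratings close in time are more alike than ratings far apart, that condition fails and the test rejects too often.

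At stake is the one Table 4 row that describes how DT1 ratings change over the month.

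**Working it through.** **1. The plan's own figure.** For a two-sided paired t-test with alpha 0.05, power 0.95 and difference/SD = 0.60 (section 5.2.1), the exact noncentral-t calculation gives power 0.9546 at n = 39 and 0.9496 at n = 38. The stated 39 reproduces. It belongs to the between-lens comparison; here it serves only as the number of completers.

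**2. Complete cases.** Inputs: 39 completers (section 5.2.2), 6 rating days (section 5.5.2), and an assumed probability m that any one day is missed, independent across days. The documents give no value for m.

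Expected complete cases = 39 × (1 − m)^6.

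| m (assumed) | (1 − m)^6 | Complete of 39 | Lost |
|---|---|---|---|
| 1% | 0.941 | 36.7 | 6% |
| 2% | 0.886 | 34.5 | 11% |
| 3% | 0.833 | 32.5 | 17% |
| 5% | 0.735 | 28.7 | 26% |
| 10% | 0.531 | 20.7 | 47% |

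These losses come on top of participants who are dispensed DT1 and stop early. The plan's own figures allow for 43 − 39 = 4 of these (4/43 = 9.3%).

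**3. False-positive rate.** With k = 6 days and n = 39, the uncorrected F-test has k − 1 = 5 and (k − 1)(n − 1) = 190 degrees of freedom. Departure from sphericity is measured by epsilon = (tr M)² / [(k − 1) tr(M²)], where M = CSC, S is the covariance of the six ratings and C is the centring matrix. Epsilon is 1 under sphericity and at least 1/5 here. A constant person effect cancels in C and leaves epsilon unchanged; what matters is serial correlation relative to day-to-day noise.

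Each setting was simulated 20,000 times with no true time effect (standard error near 5% is √(0.05 × 0.95 / 20,000) = 0.15 percentage points). All correlations are assumptions.

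| Assumed within-person structure | Epsilon | Uncorrected | Greenhouse-Geisser |
|---|---|---|---|
| Compound symmetry | 1.00 | 4.9% | 4.1% |
| Random slopes over days, plus noise | 1.00 to 0.89 | 5.0–5.6% | 4.1–4.4% |
| Person effect + serial correlation (0.80–0.95 per day) + noise (10–40% of variance) | 0.96 to 0.66 | 5.0–7.2% | 4.0–4.6% |
| Serial only, 0.5–0.8 per day | 0.96 to 0.73 | 5.1–6.8% | 4.2–4.6% |
| Serial only, 0.3–0.7 per occasion | 0.90 to 0.63 | 5.8–7.6% | 4.5–4.6% |
| Serial only, 0.8–0.9 per occasion | 0.56 to 0.50 | 8.5–9.3% | 4.9–5.2% |
| Serial only, 0.90–0.99 per day | 0.54 to 0.36 | 8.8–10.9% | 4.9–5.2% |

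Other settings with rating noise gave up to about 8%. The Huynh-Feldt correction gave about 4.7% to 5.6% throughout. A mixed model was not simulated.

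**4. Does the normality rule help?** Switching to a non-parametric test addresses distribution shape only. The usual rank analogue, Friedman's test, also needs all six ratings per participant.

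**The case against.** The case on the other side is substantial.

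- **The protocol guards against missed ratings.** Participants are told they must wear the lenses on rating days (sections 5.4.2 and 5.5.2), home ratings are reviewed at Visit 3, Table 3 includes a compliance check on their completion, and section 10 pays $20 for the home questionnaires. A miss rate of 1–3% per day is therefore plausible, and then only 6–17% of completers are lost. If misses cluster in a few people, fewer are lost than the table shows. This stands. A reader might infer that a quarter to a half of the sample will go; that needs independent miss rates of about 5–10% per day, which the documents do not support. The safeguards do not, however, bring back anyone who stops DT1 early.
- **The plan does not say that incomplete participants are dropped.** That is true. It is the default of the named method, and the plan gives no other rule.
- **The error rate may be close to nominal.** This also stands. A reader might infer from the uneven days that sphericity must fail and that the test runs at 8–10%. Uneven spacing alone does not break sphericity, and rates that high arose only when strong serial correlation was assumed with no day-to-day noise. Single-day self-ratings on a 0 to 100 scale may well carry such noise.
- **The consequence is limited.** Table 4 compares habitual lenses with DT1 by paired t-tests. Neither that comparison, nor the equivalence and superiority evaluation, nor the sample size uses this ANOVA. Agreed.

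**Conclusion.** The point holds as an inexpensive improvement to a secondary analysis. The named method, with no rule beside it, leaves out early stoppers and anyone with a missed day. Among 39 completers the expected loss runs from about 2 (at 1% missed per day) to about 18 (at 10%), with the miss rate and its independence across days assumed. Whether the remaining subset flatters DT1 cannot be determined from the documents; the discontinuation reasons in section 9 make it possible.

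The uncorrected test's false-positive rate lies between about 5% and 11%. Where it falls depends on a within-person correlation that the documents do not give, so no single figure can be attached to the plan. In the settings simulated it was at or above nominal, and the plan specifies no protection.

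A reader might go further and infer that the habitual-versus-DT1 conclusion is compromised. The documents do not support that, because this row of Table 4 concerns change over time within DT1 only.

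**What to change.** Replace the Table 4 entry with a linear mixed model on all available DT1 home ratings from every dispensed participant, with day (1, 3, 5, 7, 21, 28) as a categorical effect, unstructured covariance and Kenward-Roger degrees of freedom. The unstructured matrix has 6 × 7 / 2 = 21 parameters, so name a fallback in advance for non-convergence: a participant random effect, spatial-power correlation in days, and a separate residual noise term. Spatial-power correlation alone would leave out the person effect and the noise. Report the number of ratings available on each day.

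If the ANOVA is kept, state that a Greenhouse-Geisser correction applies. That brought the error rate to 4.0–5.2% in every setting above, but it does not recover the dropped participants; the plan should then say how incomplete ratings are handled.

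The cost is one row of Table 4, slightly more analysis work and no new data. The mixed model is valid if missingness depends only on observed ratings, which should be stated as an assumption. It also cannot use ratings from participants who take up the option in section 9 to have their data withdrawn, so their number should be reported.

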2 OBJECTIVES

The objectives of the study are:

- To examine and classify DED subtypes in a group of symptomatic CL wearers who are already wearers of daily disposable (DD) CLs (excluding Dailies Total1 (DT1)).
- To assess subjective ratings, cumulative comfort scores, average wear time and comfortable wear time while symptomatic CL wearers use their habitual DD CLs.
- To refit participants with DT1 CLs and assess subjective ratings, cumulative comfort scores, average wear time and comfortable wear time after wearing DT1 for one month.

Primary Endpoint:

- Subjective ratings of end-of-day comfort and dryness (with CLs; 0 to 100 scale)
- Average wear time (hours)
- Comfortable wear time (hours)

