- In-office subjective ratings of comfort, dryness, vision and handling (with CLs; 0 to 100 scale), total wear time and comfortable wear time (onset time of discomfort) over the last month.
- The following assessment of the study lenses will be made:
 - Distance HCHI visual acuity, OD, OS & OU;
 - Lens surface characteristics: wettability and deposition;
 - Lens fit.
- Slit lamp biomicroscopy examination (including assessments for ocular surface staining and hyperemia).
- Study exit documentation & reimbursement.

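### Table 4 repeats the between-lens tests in three DED subtypes at an unadjusted 5% level, with no exploratory label and no link to the whole-group result

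*Combined protocol and SAP*

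**What the plan says.** Table 4 (section 11.1) has two between-lens rows, "CLDEQ-8 ratings between lenses (habitual DD vs. DT1" and "Subjective ratings between lenses (habitual DD vs. DT1", each with a 2-sided paired t-test. A later row repeats them: "Comparisons as above, but on groups stratified by DED subtype (evaporative/aqueous deficient/mixed disease", again with 2-sided paired t-tests. The text above the table gives one rule for all comparisons: "statistical significance will be set at 5" per cent. There is no adjustment, testing order or exploratory label for the subtype row.

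Table 4 does not list the ratings. Section 5.5.2 describes "subjective rating 0-100 questionnaires related to comfort, dryness, vision, lens handling", and section 5.4.2 lists for Visit 3 "In-office subjective ratings of comfort, dryness, vision and handling (with CLs; 0 to 100 scale), total wear time and comfortable wear time". The primary endpoints in section 2 are "Subjective ratings of end-of-day comfort and dryness (with CLs; 0 to 100 scale", "Average wear time (hours") and comfortable wear time. Neither wear time is named in Table 4.

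The hypothesis (section 4) and the sample size (section 5.2.1) refer to the whole group. Section 5.2.2 targets 39 completers and sets no number per subtype.

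**The concern.** Read literally, section 11.1 allows any subtype comparison with p<0.05 to be called statistically significant, even when the whole-group comparison of the same item shows nothing. Several items in three small strata give many chances for this to happen by luck.

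Classifying DED subtype is the first listed objective, so subtype results will attract attention. At stake is a statement that DT1 helps on some item in some subtype, made with an error rate well above the 5% that a reader would take from section 11.1.

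**Working it through.** **1. The plan's own figure.** Inputs from section 5.2.1: two-sided alpha 0.05, power 0.95, diff/SD 0.60, difference 5 points (implied SD of the difference 5/0.60 = 8.33). Exact noncentral-t power for a paired t-test is 0.9496 at n = 38 and 0.9546 at n = 39. The stated 39 is reproduced, for one whole-group test.

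**2. Power within a subtype.** The same formula at effect 0.60, with assumed stratum sizes because the protocol gives none:

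| n in subtype | Power |
|---|---|
| 13 (one third of 39) | 51% |
| 8 | 31% |
| 5 | 18% |

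**3. Number of subtype tests.** Table 4 leaves this open, so I took several readings:
- Comfort and dryness only: 2 × 3 = 6.
- CLDEQ-8 plus comfort, dryness, vision and handling: 5 × 3 = 15.
- The same with both wear times added: 7 × 3 = 21.
- The 15-test reading with only two subtypes large enough to test: 5 × 2 = 10.

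**4. Chance of at least one p<0.05 when the lenses do not differ in any subtype.** With independent outcomes it is 1 − 0.95^k:
- k = 6: 1 − 0.95^6 = 26%
- k = 10: 1 − 0.95^10 = 40%
- k = 15: 1 − 0.95^15 = 54%
- k = 21: 1 − 0.95^21 = 66%

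Outcomes within a person are correlated, which lowers these figures. I simulated null paired differences with equal correlation between outcomes, 13 people per subtype and two-sided t-tests. Subtypes contain different people and so are independent. If p is the chance of at least one rejection within one subtype, the chance over three subtypes is 1 − (1 − p)^3, and over two it is 1 − (1 − p)^2.

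For five outcomes at correlation 0.8, p = 0.135:
- three subtypes: 1 − 0.865^3 = 35%
- two subtypes: 1 − 0.865^2 = 25%

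| Reading | Correlation 0 | 0.5 | 0.8 |
|---|---|---|---|
| 6 tests | 26% | 25% | 22% |
| 10 tests (two subtypes) | 40% | 34% | 25% |
| 15 tests | 54% | about 47% | 35% |
| 21 tests | 66% | 56% | 40% |

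If outcomes were perfectly correlated, three subtypes would still give 1 − 0.95^3 = 14%. An uneven 25/5/9 split of the 39 gives 36% to 54% for 15 tests, so the stratum sizes matter little while t-tests are used.

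**5. Results that favour DT1.** Each two-sided 5% test has a 2.5% chance of a false result in that direction. For 15 independent tests, 1 − 0.975^15 = 32%. Simulation gives about 26% at correlation 0.5 and 18% at 0.8.

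**6. Whole-group non-primary tests, for comparison.** CLDEQ-8, vision and handling are three tests: 1 − 0.95^3 = 14% if independent, and about 10% at correlation 0.8.

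**The case against.** **The size depends on inputs the protocol does not give.** This stands. The number of ratings tested, the correlation and the subtype sizes are all assumptions. A reader might infer that a false subtype finding is close to a coin toss, about 47%. That figure belongs to one scenario (15 tests, correlation 0.5), counts results in both directions, and applies only if no outcome differs in any subtype. If DT1 has a real overall effect, as section 4 hypothesises, many subtype rejections would be correct. Comfort favouring DT1 in any of three subtypes, for instance, has a null chance of only 1 − 0.975^3 = 7%.

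**All three subtypes may not be testable.** This also stands. Section 5.2.3 sets no quotas, and section 1 expects a combination of causes most often. Section 11.1 moves to Wilcoxon tests for non-normal data, and with n = 5 the smallest exact two-sided p is 2/2^5 = 0.0625, so such a subtype could not reject.

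**The plan already sets the primary analysis apart.** A reader might infer that a subtype p-value has the same standing as the primary result. The documents do not say so. Section 2 names the primary endpoints, sections 4 and 5.2.1 address the whole group, and section 11.1 confines the equivalence and superiority assessment to the primary outcomes. However, the subtype row retests primary ratings, and nothing marks those retests as lower in standing or limits what may be claimed from them.

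**This is a labelling gap in a small, minimal-risk study.** That is fair: primary endpoints, sample size and data collection are untouched. It also means the repair is cheap.

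**Conclusion.** The concern holds for the subtype row. As written, section 11.1 permits unadjusted, ungated significance claims in three subtypes. With no lens difference in any subtype, the chance of at least one p<0.05 is roughly 35% to 54% for 15 tests, about 22% to 26% for 6, and about 25% to 40% for 10 tests in two subtypes. For 15 tests, the chance of at least one false result favouring DT1 is about 18% to 32%. These ranges assume correlations from 0.8 to 0, t-tests throughout, and 39 completers divided about equally. Even the narrowest of these readings is several times 5%. Subtype power is also low, so an isolated subtype p<0.05 would be weak evidence.

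A reader might go further and infer that significance statements should also be barred for the whole-group CLDEQ-8, vision and handling tests. The documents do not support that. Those three tests carry about 10% to 14% between them and are not part of the subtype problem. Identifying them as non-primary is enough.

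**What to change.** Add to section 11.1, and label the subtype row of Table 4 to match: *DED-subtype comparisons are exploratory. They are reported as mean paired differences with 95% confidence intervals and are not declared statistically significant.*

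List in Table 4 the variables that are compared, and mark whole-group CLDEQ-8, vision and handling as non-primary.

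If a subtype significance claim is wanted, allow it only after the whole-group test of the same endpoint is significant, with Holm adjustment across the subtype tests. With 15 tests, Holm's first step compares the smallest p-value with 0.05/15 = 0.0033. Power would be limited: a subtype of 13 has 51% power at 5% and 31% even at 0.05/3. The exploratory label is therefore the more practical choice.

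The cost is one or two sentences and a table label, with no new data or participants. The small downside is that an isolated subtype p<0.05 could no longer be reported as a significant finding.

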4 HYPOTHESIS

DT1 CLs will provide equivalent or better end-of-day comfort and longer comfortable wear time for DD CL wearers who suffer from DED compared to their habitual lenses.

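### Section 11.1 plans equivalence and superiority tests on four primary endpoints at an unadjusted 5% but does not say which results would support the section 4 hypothesis

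*Combined protocol and SAP*

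**What the plan says.** Section 2 puts four variables under one primary-endpoint heading, without ranking. The first bullet holds two of them, "Subjective ratings of end-of-day comfort and dryness (with CLs; 0 to 100 scale"), and average wear time and comfortable wear time follow.

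Section 4 states the hypothesis: "DT1 CLs will provide equivalent or better end-of-day comfort and longer comfortable wear time" in daily disposable wearers with dry eye disease, compared with their habitual lenses. Dryness and average wear time are not mentioned.

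Section 11.1 says: "Differences between lenses and differences over time will be compared using either Paired t-tests or Wilcoxon matched pairs", or ANOVA, at a 5% significance level. Table 4 lists two-sided paired t-tests for the lens comparisons. After the table comes: "In addition, equivalence and superiority for the test lens (DT1) vs the habitual lens will be evaluated for the primary outcome variables". The same sentence sets the clinically relevant difference at 5 points for the ratings and half an hour for each of the two wear times.

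Section 5.2.1 sizes the study for one two-tailed paired t-test on a rating: 5 points, difference/SD 0.60, power 0.95, 39 participants.

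**The concern.** The plan gives the ingredients of a decision but no decision rule. It does not say which test decides which endpoint, whether superiority is judged against zero or against the clinically relevant difference, or whether one, two or all four endpoints must succeed. Section 4 comes closest to a rule, but 11.1 does not refer to it.

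The tests named in 11.1 also do not fit the comfort part of section 4. Equivalent or better is a one-sided, non-inferiority statement. A two-sided equivalence test has an upper limit as well, so it fails when DT1 is clearly better. A superiority test fails when the lenses are truly alike. Neither one alone answers the question asked.

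At stake is whether a reader can tell in advance which result would meet the hypothesis. If the choice is left until the data are seen, a difference on any one of four endpoints could be presented as the primary finding, and the 5% level would not apply to that claim.

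**Working it through.** **Inputs.** From the documents: four primary endpoints (section 2); 5% two-sided tests and limits of 5 points and 0.5 h (11.1); difference/SD 0.60, power 0.95 and 39 participants (5.2.1). Assumed, because the documents give none: correlations among the four paired differences, and the SD of the paired wear-time differences.

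**The plan's own figure.** Exact power of a two-sided paired t-test with n = 39 and d = 0.60 is 0.9546, and 39 is the smallest n reaching 0.95. The figure reproduces, for one rating tested against zero. The implied SD of the differences is 5/0.60 = 8.33 points.

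**If any one of four differences counted as success.** With independent endpoints the false-positive chance is 1 - 0.95^4 = 18.5%. For jointly normal differences this is also the ceiling. Counting only false results in favour of DT1, at 2.5% per test, it is 1 - 0.975^4 = 9.6%, the maximum for non-negative correlation. Simulated paired t-tests at n = 39 with equal correlation give:

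| Assumed correlation | Either direction | In favour of DT1 |
|---|---|---|
| 0 | 18.5% | 9.6% |
| 0.5 | about 16% | 7.9% |
| 0.9 | 9.5% | 4.8% |
| Single test | 5% | 2.5% |

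The inflation comes from having four endpoints. It does not come from running equivalence and superiority on the same endpoint, which have different null hypotheses.

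**If both parts of section 4 must hold.** Each part is tested by a two-sided 95% interval, so one-sided at 2.5%, and both must pass. False success is then at most 2.5% with no adjustment. Simulation at correlations 0, 0.5 and 0.9 gives 2.4% to 2.5% whichever part is false.

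**Equivalence against equivalent or better.** Take two one-sided 5% tests within ±5 points, SD 8.33, n = 39. At a true difference of 0, equivalence is shown with probability 0.958. At a true gain of 5 points, the effect the study was sized to detect, it is shown about 5% of the time. That 5% is simply the size of the test at its limit, at any n. It illustrates that equivalence alone cannot carry the comfort claim.

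**Wear time, which was not sized.** For a true 0.5 h gain at n = 39:
- SD 1.5 h: d = 0.5/1.5 = 0.33, power 53%.
- SD 2.0 h: d = 0.5/2.0 = 0.25, power 33%.
- 80% power at n = 39 needs an SD of about 1.09 h or less.

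**Holm across four co-equal endpoints.** The first step uses 0.05/4 = 0.0125. Power for one rating at d = 0.60 falls from 95% to about 86% if only that endpoint differs.

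**The case against.** The strongest reply is that no passage says any one endpoint suffices. Section 4 joins its two parts with "and", 11.1 echoes it by naming equivalence and superiority, and under that reading there is no inflation. This stands in part: the 18.5% cannot be presented as the trial's error rate. It does not close the gap, because 11.1 applies both tests to all four endpoints, does not refer to section 4, and gives dryness and average wear time no role.

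A second reply is that 18.5% is a ceiling. All four measures come from the same people and the same questionnaire, so zero correlation is unlikely, and the figure includes false results against DT1. This is right, and is why the correlated and one-directional figures are given.

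Third, some apparently missing items can be inferred. The only stated level is 5%; 5.2.1 sizes a test against zero; and section 5.5.2 collects insertion, removal and discomfort-onset times under its subjective-ratings heading, so the Table 4 row for ratings may cover wear time. These are reasonable inferences that 11.1 should state.

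Fourth, this is a single-site, non-randomized, minimal-risk study of marketed lenses with an exploratory rationale. Formal familywise control is therefore desirable rather than essential, which lowers the priority of the point.

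A reader might infer that the trial runs an 18.5% chance of a false claim for DT1, or that the design is invalid. The documents support neither: the first needs an unstated any-one rule, zero correlation and results in both directions; the second ignores that a sentence in 11.1 resolves the matter.

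**Conclusion.** The point holds and should be fixed. Section 11.1 does not say how the results on four primary endpoints decide the section 4 hypothesis, and an equivalence test alone does not show the comfort part of it.

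The size depends on how the gap is filled. If any one difference counted, the two-sided false-positive chance would be above 5%: at most 18.5%, about 16% at correlation 0.5 and 9.5% at 0.9. In favour of DT1 only, it would be at most 9.6%, falling to about 4.8% at 0.9, against 2.5%. These figures cover the difference tests only and rest on assumed correlations. If both parts of section 4 must hold, the excess disappears. The 0.95 power in 5.2.1 is correct for what it covers: one rating against zero.

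**What to change.** **In 11.1**, for DT1 minus habitual, with two-sided 95% intervals and every scale scored so that higher is better:

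1. State that section 4 is supported only if (a) the lower limit for end-of-day comfort is above -5 points and (b) the lower limit for comfortable wear time is above 0 h.
2. State that superiority is judged against zero, matching the test sized in 5.2.1. Superiority on comfort may be claimed from the same interval if its lower limit is above 0; it plays no part in the section 4 decision. Placing it after (b) in the testing order keeps 2.5% across the two superiority claims; otherwise the chance of at least one false claim is 1 - 0.975^2 = 4.9% at correlation 0.
3. Test dryness and average wear time afterwards in a stated fixed order. If all four endpoints stay co-equal instead, apply Holm to the four difference tests and still state the rule in item 1 for section 4.
4. Where equivalence is reported, use two one-sided 5% tests (90% interval within ±5 points or ±0.5 h).

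**In 5.2.1**, state that 0.95 power is for a single rating tested against zero and that wear time was not sized.

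**Cost.** These are text changes only, with three downsides to disclose. A later endpoint cannot be claimed if an earlier step fails. Comfortable wear time becomes a required step that was never sized, with 53% or 33% power for a true 0.5 h gain at the assumed SDs of 1.5 or 2.0 h. Holm, if chosen, lowers power for one rating from 95% to about 86% when only that endpoint differs.
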